CONSORT Consolidated Standards of Reporting Trials

CFR Code of Federal Regulations

CRF Case Report Form

CSOC Clinical Study Oversight Committee

DHHS Department of Health and Human Services

FDA Food and Drug Administration

FWA Federalwide Assurance GCP Good Clinical Practice

HIPAA Health Insurance Portability and Accountability Act

ICF Informed Consent Form

ICH International Conference on Harmonisation

International Committee of Medical Journal Editors ICMJE

IDF Investigational Device Exemption IND Investigational New Drug Application

IRB Institutional Review Board ISM Independent Safety Monitor

Journal of the American Medical Association AMAI. Journal of the American Dental Association JADA MedDRA®

Medical Dictionary for Regulatory Activities

MOP Manual of Procedures

Ν Number (typically refers to subjects)

National Institutes of Health NIH

OHRP Office for Human Research Protections

PHI Protected Health Information

РΙ Principal Investigator QΑ Quality Assurance $^{\circ}$ Quality Control

SAE Serious Adverse Event/Serious Adverse Experience

SOP Standard Operating Procedure

UM University of Michigan

UMHS University of Michigan Health System

US United States

PROTOCOL SUMMARY

Title: Investigation and Modulation of the Mu-Opioid Mechanisms in

Migraine (In Vivo)

Précis: This is a phase 2, single center, three-arm, double-masked,

randomized investigation and modulation of the µ-opioid mechanisms in migraine (in vivo). We will enroll 60 patients with episodic migraine (30 for the active M1 HD-tDCS group and 30 for the sham group). In addition, we will use the data from up to 10 healthy controls who were recruited and scanned during the NINDS-K23062946 project (IRBMED #HUM00027383; [name], Principal Investigator). We will then recruit healthy volunteers to a total of 30 age- and gender-matched healthy subjects. Each participant will undergo the sequence of events and evaluations laid out in the Schematic of Study Design (page viii), which will take approximately 3 months. Completion of full protocol enrollment and participation is expected to take approximately 5 years. Data will be collected on paper or electronic CRFs, or electronically on local systems (PET, MRI, QST), then transferred via HIPAA-compliant methods within the UMHS system for analysis by study staff.

Objectives: To demonstrate that clinical and experimental pain measures in

migraine patients are associated with μOR BP_{ND} in the thalamus and other pain-related regions, even during interictal phase

(non-headache phase).

To determine whether 10 daily sessions of M1 HD-tDCS have modulatory effect on clinical and experimental pain measures in

migraine patients.

To investigate whether repetitive active M1 modulation induces/reverts thalamic µOR BP_{ND}, and whether those changes are associated with clinical and experimental pain

measures in migraine patients.

Population: 60 Patients age 18-65 years (inclusive) with episodic migraine

(ICHD-3-beta); AND

30 age and gender matched healthy subjects

Subjects will be recruited from the UMClinicalStudies.org database, the clinics at the University of Michigan (UM), and

from other clinics in the region

Phase: 2

Number of Sites: 1

Study Duration: 5 YRS

Investigation and Modulation of the Mu-Opioid Mechanisms in Migraine (In Vivo) Protocol HUM00107286 Version 0.6 12 December 2018

Subject Participation

Approximately 3 Months

Duration:

Description of Agent High-de

or Intervention:

High-definition transcranial direct current stimulation (HD-

tDCS)

Estimated Time to

4 Years

Complete Enrollment:

Schematic of Study Design I:

Screening Period	Week before daily M1 HD-tDCS sessions (Neuromodulation)	Active / Sham Neuromodulation (10 Daily Sessions) M-F x2		Week after daily M1 HD-tDCS sessions	Follow-up Period ⇒
First Appt	PET/MRI Sessions	5 Daily Sessions	5 Daily Sessions	PET/MRI Sessions	Follow-up at 1 Week and at 1 Month and 2 Months Following Neuromodulation

.....

Schematic of Study Design II:

Timing (Relative to Day 0)	Procedure		
PreScreening (Up to 8 weeks prior to Day 0)	Phone Call: IRB-Approved Prescreening Checklist/Script		
Screening (Up to 3 weeks prior to Day 0)	Informed Consent Demographics History and Physical Exam Questionnaires Randomization, once subjects have been consented		
PET and MRI #1 (Up to 1 week prior to Day 0)	QST PET #1 Workup Questionnaires (PET-specific) Pregnancy Test and Drug Screen CFN (11C-carfentanil) Injection MRI #1 Screening Form (MRI-specific) MRI Questionnaires*		
HD-tDCS x 10 Daily Sessions (Day 0 - 11; Week 1 and 2)	Migraine Active Questionnaires ≤2 mA current for 20 min/day x 10 days (M-F over 2 wks)	Migraine Sham Control Questionnaires ≤2 mA current for 30 sec at start plus 30 sec at end of session x 10 days (M-F over 2 wks)	* Healthy volunteers complete participation after PET/MRI#1 visit
PET and MRI #2 (Week 3)	Questionnaires QST PET #2 Workup Questionnaires Pregnancy Test and Drug Screen CFN (11C-carfentanil) Injection MRI #2 Screening Form (MRI-specific) MRI Questionnaires		
Follow Up @ Week 1 (Week 3)	Questionnaires		
Follow Up @ Month 1 (Week 6)	Questionnaires		
Follow Up @ Month 2 (Week 10)	Questionnaires		

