5.2. SUBJECT EXCLUSION CRITERIA

An individual who meets any of the following criteria will be excluded from participation in this study:

- Presence of any other systemic or chronic pain disorder
- History or current evidence of a psychotic disorder (e.g. schizophrenia) or substance abuse; bipolar or severe major depression, as evidenced by Beck Depression score of ≥ 20*
- Prior use of tDCS
- Ongoing, unresolved disability litigation
- History of neurological disorder (e.g. epilepsy, stroke, neuropathy, neuropathic pain)
- Current use of opioid pain medications
- Allergic response to study radiotracers or chemically-related drugs
- Excluded by MRI Center or PET Center safety screening checklist (as administered by study staff)
- Female participants who are pregnant, nursing, or planning a pregnancy, or who are of childbearing potential and are not using a reliable means of contraception during the baseline and study periods (negative urine pregnancy test must be available before any procedures are initiated)
- Treatment with an investigational drug, device or other intervention within 30 days of study enrollment (Screening Visit).
- Anything that would place the individual at increased risk or preclude the individual's full compliance with or completion of the study (eg, medical condition, laboratory finding, physical exam finding, logistical complication).

^{*} The Beck Depression Inventory will be graded by study staff at the time of completion. Individuals with a score of ≥ 30 will be provided with a pamphlet from the Michigan Depression Center that contains information and contacts regarding depression. In addition, those individuals who respond to question #9 with answers #2 or #3, will be provided with a flyer from the Department of Health and Human Services National Suicide Prevention Lifeline (800 number and website).

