5.3. STRATEGIES FOR RECRUITMENT AND RETENTION

We will recruit 60 episodic migraine patients divided into 2 groups: 30 for the active M1 HD-tDCS group and 30 for the placebo HD-tDCS group. In addition, we will use the data from up to 10 healthy controls who were recruited and scanned during the NINDS-K23062946 project (IRBMED #HUM00027383; [name], Principal Investigator). We will then recruit healthy volunteers to a total of 30 age- and gender-matched healthy subjects.

Recruited patients will be screened from the UMClinicalStudies.org (formerly Engage) recruitment network and the University of Michigan. In addition to active referral from pain centers, advertisements will be placed in other pain clinics in the region. In-hospital advertisements will also be placed in pain clinics and departments at the institution, as well as across the university.

Subjects recruited will be prescreened by phone using an initial IRB-approved questionnaire. Those who pass the phone screening will be scheduled for an in-person Screening Visit, which will commence with a verbal and written informed consent process. Once informed consent has been obtained, subjects will undergo further screening by obtaining a history and performing a physical exam and QST. Those subjects who are determined to be eligible to enter the study will be enrolled into either the migraine or healthy volunteer pools; if migraine, they will be randomized to active or sham treatment.

Study duration per subject is expected to be less than 3 months; however due to the scheduling of PET and MRI visits, visit reminders (eg, phone and/or email; subject preference) may be implemented to help with retention.

During the course of participation, subjects will be compensated according to amounts stated in the informed consent form and approved by the IRB.

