5.4. TREATMENT ASSIGNMENT PROCEDURES

5.4.1. RANDOMIZATION PROCEDURES

Participants initially will be screened by phone. After clinical exam and diagnosis of episodic migraine (confirmed by IHS/ICHD-3-beta criteria) participants will be randomized to the treatment HD-tDCS or sham groups using the Taves covariate adaptive randomization method. Using this method, a new participant will be sequentially assigned to a group based upon the previous assignments of other participants and certain covariates. The first eight migraine participants will be randomized by coin flip and the remaining migraine participants will be randomized by age and gender, following the Taves covariate adaptive randomization protocol. Healthy volunteers will be age- and gender-matched to the earlier enrolled participants.

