7.3. INTERMEDIATE VISITS

PET #1 (Day -21 to Day -1)

The PET scan will ideally take place during the week prior to the initial HD-tDCS session. The 21 day window allows for scheduling of the PET and MRI visits within three weeks of each other.

MRI #1 (Day -21 to Day -1)

The MRI will ideally take place during the week prior to the initial HD-tDCS session. The 21 day window allows for scheduling of the PET and MRI visits within three weeks of each other.

HD-tDCS #1-10, Day 0-4 and 7-111

On DAY 0, HD-tDCS will begin. Subjects will have been randomized prior to Day 0, but after consent has been provided.

PET #2 (Day 16 ± 2)

PET Scan #2 will take place during the week following HD-tDCS. If it cannot be scheduled during this week, it may be completed during the following week.

MRI #2 (Day 16 ± 2)

MRI #2 will take place during the week following HD-tDCS. If it cannot be scheduled during this week, it may be completed during the following week.

¹ M-F; missed days can be doubled within (M-F) x 2 schedule and with study team approval

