APPENDIX A: SCHEDULE OF EVENTS

APPENDIX B: QUESTIONNAIRES

APPENDIX A: SCHEDULE OF EVENTS

Procedures	Phone PreScreening (Dav –56 to -22)	Screening (Day-21 to -1)	PET/MRI #1 (Day -21 to -1)	HD-tDCS #1-10 (Days 0-4 & Days 7-112)	PET/MRI #2 (Day 16 ± 2)	Follow Up Week #1 (Day 16 ± 2)	Follow Up Month #1 (Day 37 ± 2)	Follow Up Month #2 Day 65 ± 2)	Early Termination ³
Prescreening Script/Checklist	X								Ш
Informed Consent		X							
Adverse Events		X	X	Х	Х	X	Х	Х	X
Medical/Dental History and Physical		X							
Medication History/ Concomitant Medications		X	X	Х	Х	X	х	Х	
Pregnancy Test (Dipstick) and Drug Screen ⁴			PET Only		PET Only				
Quantitative Sensory Testing (QST)			Х		Х				
Eligibility Assessment ⁵		X							
RANDOMIZATION		X ⁶	X ₆						
PET			X		Х				
Sustained Thermal Pain Threshold Stress (STPTS) PET Challenge			X		х				
Blood Sampling ⁷ Single Draw, Genetics Serial Samples, Biomarkers			PET Only		PET Only				
MRI			Х		Х				\square
HD-tDCS (M-F for 2 weeks)				10X8					

² Missed days can be doubled within the (M-F) x 2 schedule and with study team approval

³ If subject completes an in-person visit

⁴ Safety screen for ¹¹C-carfentanil

⁵ Schedule subject visits and provide subject with instructions (PET & MRI)

⁶ Subjects will be randomized after they have met eligibility and have been consented. This will occur prior to Day 0 ⁷ If subject has consented to sample future use sub-study.

⁸ See Section 6 for active vs healthy volunteer treatment paradigm

Procedures	Phone PreScreening (Dav –56 to -22)	Screening (Day -21 to -1)	PET/MRI #1 (Day -21 to -1)	HD-tDCS #1-10 (Days 0-4 & Days 7-11 ²)	PET/MRI #2 (Day 16 ± 2)	Follow Up Week #1 (Day 16 ± 2)	Follow Up Month #1 (Day 37 ± 2)	Follow Up Month #2 Day 65 ± 2)	Early Termination ³
Questionnaires									
Demographics		X ₉							
MIDAS Questionnaire		X ₉							
Beck Depression Inventory		X ₈							
"Expectation of Effect"		X							
McGill Pain Questionnaire (Long Form)		X							
McGill PQ (Short Form)		X	X	X	Х	Х	X	Х	
PANAS ⁹		X ₉	X ₉	X	Х	Х	X	Х	
GeoPain (via iPad)8		X	X	X	Х	Х	Х	Х	
Visual Analog Pain Scale ⁸		Х	X	X	Х	Х	Х	Х	\Box
Allodynia Questionnaire		Х	Х		Х	Х	Х	Х	\square
PET Subject Information Sheet			X ₉		Х				┌┤
Pittsburgh Sleep Quality Index		X ⁹				Х	Х	Х	
tDCS AE Questionnaire				X	Х	Х	Х	Х	┌┤
H.O.P.E. Questionnaire						X	X	Х	

⁹ At Screening, Before and After MRI/PET Scans and tDCS Sessions, and at Follow Up Visits

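### Allocation is minimised on age and gender, but no main active-versus-sham model is committed to both factors; the likely cost is lost precision in a secondary comparison, not bias

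*Combined protocol and SAP*

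**What the plan says.** **Allocation.** Section 5.4.1 uses the Taves covariate-adaptive method. The first eight migraine patients are assigned by coin flip; after that, "the remaining migraine participants will be randomized by age and gender".

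**Analysis.** Section 11 lists t-tests or ANOVA, or ANCOVA with age, as ways to model the effects of interest, including active or sham stimulation. It adds a global model with sex and age as nuisance or interaction variables, and links that approach to the HD-tDCS effect on receptor binding. In Section 11.1, Aims 1 and 3 each have an analysis paragraph. Aim 3's names age but not sex, and describes change from before to after active treatment. Aim 2, the active-versus-sham comparison of clinical and experimental pain, has none. Section 11.2 sizes Aims 1 and 2 on a two-group t-test without covariates. Section 11.6 defers the final analysis to a separate Statistical Analysis Plan.

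**Timing of assignment.** The statements agree that assignment follows consent and precedes Day 0, but differ on the visit and the condition:
- Schematic of Study Design II, Screening row: "Randomization, once subjects have been consented".
- Section 5.3: "Those subjects who are determined to be eligible to enter the study will be enrolled into either the migraine or healthy volunteer pools", with migraine patients then randomised.
- Section 5.4.1: "After clinical exam and diagnosis of episodic migraine".
- Section 7.3: "Subjects will have been randomized prior to Day 0, but after consent has been provided".
- Appendix A ticks randomisation at both Screening and PET/MRI #1, with the footnote "Subjects will be randomized after they have met eligibility and have been consented. This will occur prior to Day 0".

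Appendix A ticks the eligibility assessment at Screening only, and marks the row "Pregnancy Test (Dipstick) and Drug Screen" for PET visits only. Section 5.2 says a "negative urine pregnancy test must be available before any procedures are initiated". Section 9.1 counts the pregnancy dipstick among the consent and screening processes.

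**The concern.** Minimisation makes the arms more alike on age and sex than simple randomisation would. If those factors predict the outcome, the true sampling variance of the difference between arms shrinks. A t-test that ignores them still estimates its standard error as if the allocation had been unrestricted. The standard error is then too large, the test rejects too rarely under the null, and the precision that balancing was meant to secure is not used. Putting the same factors in the model restores the nominal level and recovers the power.

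The plan treats sex as relevant: Section 11 selects regions known to be involved in sex differences in pain regulation. For Aim 2, though, neither factor is committed to the model. A list of permitted tests with no named main one also leaves the choice open until the data are in.

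At stake is the active-versus-sham comparison, which Section 3.4 places among the secondary outcomes. The primary comparison of migraine patients with controls (Section 3.3) does not involve the minimised allocation.

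**Working it through.** **The plan's own figure.** Section 11.2 gives 24 per group, 80% power, effect size 1.2, two-sided 0.05.
- Dropout reproduces: 24/(1 − 0.20) = 30 per group.
- Power does not. With 24 per group the noncentrality at 1.2 is 1.2 × √(24/2) = 4.157, and t-test power is 98.3%. The effect detectable with 80% power is 0.826 SD; 12 per group would give 80.2% at 1.2. That mismatch is a separate matter, but because of it both 0.83 and 1.2 are shown below.

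**Inputs.** From the documents: 60 patients in two arms, eight coin flips, minimisation on age and gender, ages 18–65, women to men 3:1 (Section 14.4), 20% dropout leaving 48. Assumed, because the documents are silent: the share R² of outcome variance explained by age and sex (10% or 25%, split equally), age uniform over 18–65, two to five equal age bands, and ties broken by coin flip.

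**Approximate check.** With perfect balance the true standard error is √(1 − R²) times the one the t-test uses.
- Unadjusted type I error is P(|Z| > 1.96/√(1 − R²)). For R² = 10%: 1.96/0.949 = 2.066, or 3.9%. For 25%: 1.96/0.866 = 2.263, or 2.4%.
- Adjusted effect in residual SD units at 0.83: 0.83/0.949 = 0.875 and 0.83/0.866 = 0.958. With 24 per arm and 44 degrees of freedom, power is 84.2% and 90.1%, against 80.4% at 0.83 for the plain t-test.

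Balance is never perfect, and dropout loosens it, so simulation should give somewhat smaller effects.

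**Simulation.** 20,000 trials per setting; the Monte Carlo standard error of a 5% rate is √(0.05 × 0.95/20,000) = 0.15 points. Ranges are over the two to five age bands.

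| Type I error | R² = 10% | R² = 25% |
|---|---|---|
| 60 analysed, unadjusted | 3.7–4.3% | 2.5–2.9% |
| 48 analysed, unadjusted | 4.2–4.4% | 3.1–3.3% |
| 48 analysed, age only | 4.5–4.7% | 3.7–4.0% |
| 48 analysed, age and sex | 5.0% | 5.0% |

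| Power at 0.83 SD, 48 analysed | Unadjusted | Age and sex |
|---|---|---|
| R² = 0 | 79.8–80.0% | 79.2–79.5% |
| R² = 10% | 80.4–81.0% | 83.2–83.6% |
| R² = 25% | 81.7–82.7% | 89.3–89.9% |

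At 1.2 SD with 48 analysed (6,000 trials, three bands), unadjusted against adjusted power is 98.1% and 98.1% at R² = 0, 98.4% and 98.8% at 10%, and 99.0% and 99.7% at 25%.

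**Timing.** The rate of loss between assignment and Day 0 is not given. At an assumed 2%, 5% or 10%, unrelated to arm, the mean difference in arm size is 1.0, 1.5 or 1.9 patients if assignment comes before the checks, and about 0.7 if it comes after. Power differs by 0.01, 0.03 and 0.05 points.

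**The case against.** The strongest reply has four parts.

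1. Section 11 does not leave sex out. Its global model names both sex and age, is stated as planned, and is tied to the HD-tDCS effect on receptor binding. This stands for the PET outcomes. It does not cover Aim 2's clinical and sensory outcomes, and it is additional to the listed tests, not named as the main analysis.
2. Covariates belong in the Statistical Analysis Plan, which the protocol lists as a separate document. It may already name them. The point is therefore conditional on that plan.
3. At the protocol's stated effect size of 1.2, adjustment gains under 1 point of power. That is correct. The larger gains apply near 0.83 SD, the effect that 24 per arm detects with 80% power.
4. The error is in the safe direction. This also stands.

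Two stronger readings are tempting. A reader might infer that an unadjusted analysis would be biased or would inflate false positives; the calculation shows the reverse. A reader might also infer that patients are assigned before eligibility is known, so that PET-day exclusions distort the comparison. The documents permit that sequence but do not require it: Appendix A's footnote makes eligibility a condition, randomisation is also ticked at PET/MRI #1, and Sections 5.2 and 9.1 tie the pregnancy test to what precedes study procedures. Another Appendix A footnote labels the test row as a safety screen for the tracer, and no section makes a positive drug screen an exclusion in itself.

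**Conclusion.** The point holds as a gap in specification. The minimisation factors are age and gender, and no main active-versus-sham model in the protocol is committed to both; the gap is clearest for Aim 2. If the factors are prognostic to the assumed degree, the unadjusted test runs at about 4% or 3% and gives up about 3 or 7 points of power at 0.83 SD. If they explain nothing, the t-test loses nothing and adjustment costs under 1 point. These sizes rest on assumed variance shares, age distribution and banding, none of which the documents give. The consequence is limited to precision in a secondary comparison.

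The differing statements on assignment timing are an inconsistency of wording with negligible effect on power.

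**What to change.** State in Section 11, or confirm in the Statistical Analysis Plan, that every active-versus-sham model includes age and sex as covariates, with Aim 2's clinical and QST outcomes named explicitly. Add an analysis paragraph for Aim 2 that identifies this as its main model. The cost is a few sentences and two degrees of freedom.

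For consistency only, reconcile Schematic II, Sections 5.2, 5.3, 5.4.1, 7.3 and 9.1, and Appendix A on when assignment occurs and when the pregnancy test is done, so that assignment follows completion of the eligibility checks and precedes Day 0. This needs amendment wording and some scheduling care but no extra visit, because nothing scheduled before Day 0 depends on the arm.

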1. KEY ROLES

Individuals: Principal Investigator: [name], DMedSc

Institutions: Program Official: [name]

2. INTRODUCTION: Background Information And Scientific Rationale 2.1. BACKGROUND INFORMATION

Migraine is a debilitating chronic condition that affects most of the patient's existence, from childhood to late adulthood. During frequent headache attacks, its sufferers show marked increased sensitivity to noxious (hyperalgesia) and even non-noxious stimuli, a phenomenon called cutaneous allodynia that affects 63% of the patients (Bigal et al., 2008b). Although MRI-based techniques have provided insights into some brain mechanisms of migraine (Granziera et al., 2006; DaSilva et al., 2007a; DaSilva et al., 2007b), many questions regarding its molecular impact in the brain are still unanswered. The overall goal of this project is to provide a detailed understanding of the μ -opioid receptor mediated transmission in the brain of migraine patients, one of the most important central pain regulatory systems in humans, with the long-term objective of developing more focused neuromechanism-driven methods for migraine research and therapy.

2.2. RATIONALE

Preliminary studies from our NIH-NINDS K23 project using positron emission tomography (PET) with [11C] Carfentanil, a selective radiotracer for µ-opioid receptor (μOR), have indicated that there is a decrease in μOR availability (non-displaceable binding potential BPND) in the brain of migraine patients during the headache attacks and allodynia, including areas like thalamus and periagueductal gray matter (PAG) (DaSilva et al., 2014a; DaSilva et al., 2014b; Nascimento et al., 2014). µOR BPND is an objective measurement in vivo of endogenous µ-opioid availability, and its acute reduction reflects the activation of this neurotransmitter system (Zubieta et al., 2001). This is arguably one of the neuromechanisms most centrally involved in pain regulation, affecting multiple elements of the pain experience (Zubieta et al., 2002). Moreover, MRIbased reports have found that those findings co-localize with neuroplastic changes in migraine patients (DaSilva et al., 2007a; DaSilva et al., 2007b). Conventional therapies are unable to selectively target those dysfunctional brain regions, and there is a paucity of data on how to reverse embedded neuroplastic molecular mechanisms when available medications and surgical therapies fail. Interestingly, several studies with motor cortex stimulation (MCS) have shown that epidural electrodes in the primary motor cortex (M1) are effective in providing analgesia in patients with refractory central pain (Lima and Fregni, 2008). The rationale for MCS stimulation is based in part on the thalamic dysfunction noticed in chronic pain and migraine (Lenz et al., 2004), and also on studies demonstrating that MCS significantly changes thalamic activity (Garcia-Larrea et al., 1999). Evidently, the invasive nature of such a procedure limits its indication to highly severe chronic pain disorders. New non-invasive brain neuromodulatory methods for M1, such as transcranial direct current stimulation (tDCS), can now safely modulate and activate the µOR system (DosSantos et al., 2012; DosSantos et al., 2014), providing relatively lasting pain relief in chronic pain patients and migraine (DaSilva et al., 2011c; DaSilva et al., 2011b)

(http://www.jove.com/details.php?id=2744). However, the electric fields generated by its most conventional analgesic montage are widely spread across the brain, lacking specificity on the pain-related structures directly targeted. Recently, a novel high-definition tDCS (HD-tDCS) montage (Villamar et al., 2013) created by our group was able to reduce exclusively "contralateral" sensory-discrimative clinical pain measures (pain intensity/area) in chronic patients by targeting more precisely the putative M1 region.

